## 3.12. Interim Analyses

No interim analyses are planned for this study.

#### 4. STUDY ANALYSES

### 4.1. Subject Disposition

A tabulation of the disposition of subjects will be presented by treatment assignment and overall. The number screened, the number randomized, the number treated in each arm, and the reasons for study discontinuation will be reported. Summaries of the number in each analysis set will be presented. Entry criteria and protocol deviations will be listed. Screen failures will be listed.

A by-subject data listing of study completion information including the reason for premature study withdrawal, if applicable, will be presented.

### 4.2. Demographics and Baseline Characteristics

Demographic and baseline characteristic data summarization will be performed in order to descriptively assess the comparability of treatments. Summaries will be generated for the ITT, Safety and PP populations. Data to be tabulated will include age (continuous and classified <30/>>=30), sex, child-bearing potential (for females only), race, ethnicity, height, weight, BMI (continuous and classified as underweight (<20), normal (20-<25), overweight (25-<30), and obese (>=30))and smoking history as well as baseline characteristics related to medical history. Weight, BMI, and age will be analyzed as a continuous variable using descriptive statistics (number of subjects, mean, SD, median, minimum, and maximum). Age category, sex, race, ethnicity, BMI category, and smoking status will be summarized by frequency (count and percent). Selected baseline variables will be compared to assess the balance of characteristics across the treatment groups. Age and BMI will be compared using ANCOVA.

Demography, general medical history, and smoking history will be presented in data listings.

Medical history will be coded using MedDRA v20.0, and the number and percentage of patients experiencing at least 1 such diagnosis by MedDRA System Organ Class (SOC) and preferred term (PT) will be reported.

## 4.3. Efficacy Evaluation

Efficacy analyses will be conducted using the ITT and PP populations. In the event that these two populations are the same, only the ITT tables will be produced.

#### 4.3.1. EASI, IGA, VAS

EASI, IGA, and VAS scores will be summarized using descriptive statistics at Baseline, Day 14, Day 28, and Day 42 for actual values and change-from-baseline values. Tabulations will be produced for both the ITT and PP populations.

The difference in treatment groups in change-from-baseline values at post-baseline visits will be analyzed using a mixed model Analysis of Variance with one between-subject variable (active group vs. vehicle group) and one within-subject variable (Day 14, Day 28, and Day 42).

The interaction between within-subject and between-subject variable will be included in the mixed model to test if any difference in treatment groups at post-baseline visits.

The model will include treatment group, siteid and visit as the independent effects and the interaction term treatment group\*visit\*siteid. Outputs from the analysis will include the p-value

for the treatment group and interaction factor separately. The p-value should be evaluated at a significance level of 0.05.

Mixed model ANOVA will be implemented using PROC GLM in SAS using the REPEATED option.

Additionally, a one-sided two-sample equal-variance t-test will be performed as a supportive test to analyze the differences in mean change in scores from baseline between treatment groups at each post baseline visit (Day 14, Day 28, Day 42). Output from the analysis will include a one sided 95% confidence interval and p-value. The p-value should be evaluated at a one-sided significance level of 0.025.

The above analysis will also be performed by subgroups – age, gender, and race for the ITT Population.

An exploratory analysis will also be conducted by the number of AD sites (1, 2 and >2) the subjects had.

At each visit, based on the score, subjects will be categorized into the below categories.

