4 ENDPOINTS

4.1 Safety & tolerability:

• Safety and tolerability endpoints will consist of all adverse events reporting during the study duration.

4.2 Efficacy:

Difference in Atopic Dermatitis Area Severity Index (EASI) Score from Baseline to Day 28

4.3 Exploratory:

- Difference in Visual Analog Scale (VAS) Score for Pruritus from Baseline to Day 28
- Difference in the Skindex 16 Score from Baseline to Day 28
- Difference in the IGA score from Baseline to Day 28
- Difference in Actigraphy Movement Count per Hour and sleep quality during the night from Baseline to Day 28
- Difference in biomarkers between active and vehicle groups
- Composition of microbiome
- Difference in skin microbiota from baseline to Day 28 between active and vehicle groups
 - Observing a difference in Staphylococcus aureus and a more diverse microbial collection on the patient's skin.

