5 STUDY DESIGN

- This is a Prospective, Vehicle Controlled, Double Blind, Multicenter, Randomized Phase II trial, comparing the effect of twice daily B244 application for 28 days vs vehicle application on treatment of mild to moderate AD
- We will enroll approximately 130 patients and complete 104 patients
- After screening and recruitment, participants will be randomized to active or vehicle application for 28 days.
- Subjects will apply a total of 8pumps of IP per application to all affected areas twice-a-day (i.e. 8pumps in the morning and 8pumps again at night) for 28 days.
- Subjects will be provided with cleanser and moisturizer to use for the duration of the study
- Randomization will be 1:1 so that equal number of patients will be treated in each Arm of the study.
- All B244 randomized subjects will be treated at the dose of 4x10⁹ cfu/ml
- Screening will occur at Days -21 to -14
- Washout will occur after Screening visit (Days -14 to -1)
- Randomization will occur during the baseline period for the study
- Clinical assessments of response to treatment will be made at Baseline, Study Days 14 and 28.
- Subject will come back for the final visit on Study Day 42
- Safety evaluations will consist of review of participant's medical history at screening and on-going assessment of adverse events reported throughout the study duration.

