8.15 Lifestyle Restrictions

8.15.1 Use of cleanser and moisturizer during the trial

At the beginning of the trial, subjects will be provided cleanser and moisturizer to use for the duration of the trial as needed. Subjects will be asked not to use any other cleansers, or moisturizers during the course of active treatment. (Baseline-Day 28). Although moisturizer is provided to subjects, its use it not mandatory in the study and may be used when and as needed only. If subjects do not have the need to use the moisturizer, they may forego its use all together.

Although study cleanser is provided, subjects will be asked to refrain from washing the treatment areas with study cleanser starting from Washout through Day 28. Subjects may use cleanser to wash other parts of their body not treated during the study. At Day 28 (end of study drug application) subjects will be asked to return cleanser that were provided to them by the sponsor and will be asked to go back to their regular regimen and use their preferred cleanser.

Provided moisturizer may be applied to the application site AFTER IP administration. Subject should apply the IP as instructed, let the site of application dry and only then apply the moisturizer.

Subjects may not wash application area with cleanser and water AFTER each application.

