- 6. Weight of an IP kit will be obtained at the at the Baseline visit. Study staff will be asked to weigh 2 bottles without the carton box PRE FIRST DOSE. Weight will be recorded in grams. Subjects will be asked to bring both bottles back for the Week 2 and Week 4 visit. Upon return for the study visit, 2 bottles will be weighted again.
- 7. Subjects will be asked to apply the IP twice daily. First IP application will happen in the office under medical supervision.
- 8. AEs will be monitored throughout the trial, starting with the time ICF has been signed.
- 9. Cleanser and moisturizer should be returned to the study coordinator. Subjects will be asked to go back to their regular routine.
- 10. Actigraphy watch is dispensed at the Baseline visit. Subjects will be asked to wear one watch on each wrist starting at Baseline and through Day 28 visit. Subjects are allowed to take watches off during bathing/swimming/showering but will be asked to put watches back once these procedures are completed.
- 11. Patients should fast for at least 8 hours before the test. Blood for clinical chemistry will be shipped to the central lab for processing. Chemistry, Hematology, HbA1C, Lipid Panel and Angiotensin converting enzyme tests will be done at Screening, Week 2, Week 4 and Week 6. Serology will only be done at Screening. Kits and lab manuals will be provided by the Cenetron Labs.
- 12. Blood samples for biomarkers will be collected and processed on site within 5 minutes of collection. Patients should fast for at least 8 hours before the test. Samples will then be frozen onsite and shipped on monthly bases to the Central lab for storage.
- 13. Blood pressure readings will be obtained at every visit. Subject should be allowed to rest for > 5 minutes sitting, then serial clinic BP measurements and heart (x3) rate will be performed, using the non-dominant arm with a calibrated electronic sphygmomanometer. The average of the second and third readings will be documented.
- 14. Moisturizer to be used for the duration of the trial will be provided to all subjects starting with the Washout period. Subjects will be asked to refrain, if possible, from using any other moisturizer and apply the provided product while they are participating in the trial. Any left over moisturizer will be collected at Week 4 visit.

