### 1.2.4. Efficacy, Safety and Exploratory Parameters

### 1.2.4.1. Efficacy Parameters

The efficacy endpoint includes:

x Difference in Atopic Dermatitis Area Severity Index (EASI)

The following exploratory endpoints are considered as part of the efficacy analyses:

- x Difference in Visual Analog Scale (VAS) Score for Pruritus from baseline to post-baseline visits
- x Difference in the Skindex 16 Score from Baseline to post-baseline visits.
- $\bar{x}$  Difference in the IGA Score from Baseline to post-baseline visits.
- ∑ Difference in Actigraphy Movement Count per Hour and sleep quality during the night from Baseline to Day 28
- $\overline{x}$  Difference in biomarkers between active and vehicle groups
- **X** Composition of microbiome
- ☑ Difference in skin microbiodata from Baseline to Day 28 between active and vehicle groups.
- X Observing a difference in Staphylococcus aureus and a more diverse microbial collection on the patient's skin.

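### The main efficacy model averages the off-treatment Day 42 visit into its treatment p-value, so it does not test the Day 28 endpoint on which the trial was sized, and the SAP endpoint list loses Day 28 without recording the change

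*SAP*

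**What the plan says.** **Endpoint.** Protocol 4.2 defines the efficacy endpoint as "Difference in Atopic Dermatitis Area Severity Index (EASI) Score from Baseline to Day 28". Protocol 4.3 uses the same Day 28 time for VAS, Skindex 16 and IGA. Protocol 15.1 and SAP 3.1 compute the sample size from Day 28 changes in EASI.

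**Visits that count as response.** Protocol 5 states "Clinical assessments of response to treatment will be made at Baseline, Study Days 14 and 28", and SAP 1.2.1 repeats it. Day 42 is described only as the final visit. The assessment schedule in the Clinical Trial Summary puts that visit 14 (±3) days after the last dose. Product-free skin care changes too: at Day 28 subjects "will be asked to go back to their regular regimen and use their preferred cleanser" (Protocol 8.15.1). Appendix A, footnote 9, on returning cleanser and moisturizer, adds "Subjects will be asked to go back to their regular routine".

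**Main model.** SAP 4.3.1 analyses change from baseline with a treatment factor and "one within-subject variable (Day 14, Day 28, and Day 42" as levels. It is fitted by PROC GLM with REPEATED, and the treatment p-value is read at 0.05. Protocol 15.4.5 has the same three post-baseline visits, plus Baseline as a level. Both documents then add a one-sided t-test at each visit and label it supportive.

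**SAP endpoint list.** SAP 1.2.4.1 gives EASI no time point. VAS becomes "Difference in Visual Analog Scale (VAS) Score for Pruritus from baseline to post-baseline visits" and IGA becomes "Difference in the IGA Score from Baseline to post-baseline visits". Skindex 16 is worded the same way, while actigraphy keeps Day 28. SAP Section 5 records the per-protocol redefinition and the deferral of biomarker and microbial data, but not this change.

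**The concern.** The endpoint, the sample size and the main test should describe one quantity. Here the first two refer to Day 28, and the third refers to an average that includes a visit with no study product and a different background skin-care routine.

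If benefit fades after spraying stops, the average understates the on-treatment difference and the main p-value may miss an effect that is present at Day 28. If the arms separate mainly after Day 28, the main p-value may be positive with little support from the endpoint visit. Neither document says which result governs if the model and the Day 28 t-test disagree. With the endpoint list also stripped of Day 28, a reader of the SAP alone cannot tell which visit carries the efficacy claim.

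**Working it through.** **1. The plan's own figure.** Inputs from Protocol 15.1 and SAP 3.1: difference (−1.4) − (−5.3) = 3.9, SD 7.0, 52 per arm, one-sided alpha 0.025, equal-variance t-test.

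- Standard error = 7.0 × √(2/52) = 1.373
- Noncentrality = 3.9 / 1.373 = 2.84, on 102 degrees of freedom
- Power = 80.3% (51 per arm gives 79.6%), and 104 / 0.8 = 130 randomized

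The stated power of more than 80% reproduces, for Day 28 alone.

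**2. What the main model tests.** The between-subject test in PROC GLM REPEATED is on the equally weighted mean of the repeated visits. The SAP does not state weights; this follows from the procedure it names. The tested difference is (d14 + d28 + d42) / 3, so one third of the weight falls on Day 42. With SD 7.0 for each change and a common correlation ρ between visits, the SD of the mean is 7.0 × √((1 + 2ρ)/3).

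**3. Illustration.** The documents give no Day 14 effect, Day 42 effect or ρ. Assume ρ = 0.6 and a Day 14 effect 75% of Day 28, and ignore the site terms. The SD of the mean is 7.0 × √(2.2/3) = 5.99, and the standard error is 5.99 × √(2/52) = 1.176. A two-sided 0.05 test has essentially the same power as one-sided 0.025 here.

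| Day 42 effect kept | Averaged difference | Noncentrality | Power |
|---|---|---|---|
| 0% | 3.9 × (0.75 + 1 + 0)/3 = 2.275 | 1.94 | 48% |
| 50% | 3.9 × (0.75 + 1 + 0.5)/3 = 2.925 | 2.49 | 69% |
| 100% | 3.9 × (0.75 + 1 + 1)/3 = 3.575 | 3.04 | 85% |

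The average matches Day 28 alone when (1.75 + f)/3 ÷ 5.99 = 1/7.0. This gives f = 3 × 5.99/7.0 − 1.75 = 0.82. Under these assumptions pooling loses power unless about 82% of the effect persists two weeks off product.

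**4. Range.** With ρ from 0.4 to 0.8 and a Day 14 effect of 50–100%, a zero Day 42 effect gives 33% (1.95/1.278 = 1.53) to 68% (2.60/1.063 = 2.45). Full persistence gives 71% (3.25/1.278 = 2.54) to 95% (3.90/1.063 = 3.67). Widening to ρ from 0.3 to 0.9 and persistence of 0–100%, the averaged difference runs from 1.95 to 3.90 and power from 31% to 97%.

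**5. Can the planned output show the discrepancy?** Only in part.

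- The SAP text calls for a treatment-by-visit interaction, but the only interaction in its model statement is treatment by visit by site. No clean term shows whether Day 42 departs from Day 28.
- GLM REPEATED drops a subject who lacks any of the three visits, so someone seen at Day 28 but not at Day 42 leaves the main test.
- The shell for Table 14.2.1.1 prints the mixed-model p-value inside each visit block, where it could be read as a Day 28 result.

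**The case against.** The strongest reply is that this is the protocol's own plan. Protocol 15.4.5 already puts Day 42 in the mixed ANOVA, Protocol 14 lists Day 42 among the EASI comparisons, and the protocol objectives (3.2, 3.3) already speak of post-baseline visits. All of that stands. A reader might infer that the SAP introduced the pooling; it did not. What the SAP alone changed is the endpoint wording. The conflict therefore also lies inside the protocol, between Section 4 on one side and Sections 3 and 15.4.5 on the other.

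A reader might also infer that Day 28 has vanished from the analysis. It has not. SAP 4.3.1 keeps a Day 28 t-test with an interval, the improvement proportions are tested at Day 28, the tables report by visit, and the per-protocol population requires the Day 28 visit. The remaining gap is one of rank: the test that matches the endpoint is the supportive one.

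Nor do the documents support saying that the p-value no longer measures response to treatment. Two of the three visits are on treatment. Type I error under no difference at any visit is unaffected by the pooling, and both randomized arms resume usual skin care alike. That return should not be read as a return to atopic dermatitis drugs either, because Protocol 8.13 prohibits the listed therapies for the duration of the trial.

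Finally, safety is the primary objective, and Protocol 15.4.5 calls efficacy p-values exploratory. This limits the weight of the point but does not remove the mismatch.

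**Conclusion.** The point holds as a mismatch between the stated endpoint and the main test, present in both documents, together with an unrecorded change of endpoint time in the SAP.

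Its size cannot be fixed from the documents. On the assumptions in the working, the three-visit test has about 48%, 69% or 85% power at 0%, 50% or 100% persistence, against 80.3% for Day 28 alone. A reader might infer that pooling necessarily costs power. It does not: no passage says whether benefit fades or persists off product, and the sign depends on that. What does not depend on those assumptions is that the main treatment p-value is not a test of the Day 28 difference. The correction is worth making before analysis, but as a matter of alignment in an exploratory efficacy analysis, not as a threat to the trial's validity.

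**What to change.** 1. In SAP 1.2.4.1, restore the Baseline-to-Day-28 time for EASI, VAS, Skindex 16 and IGA. If the wider wording is intended, list and justify it in SAP Section 5.
2. In SAP 4.3.1–4.3.2 and Protocol 15.4.5, name the Day 28 treatment contrast as the main efficacy result. For EASI this is the comparison that the sample size already supports.
3. Report Day 42 in its own table or block, labelled as follow-up about 14 days after the last dose with usual skin care resumed.
4. In the table shells, mark any model p-value that spans visits as such, so that it is not read as a Day 28 result.

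The cost is wording in two documents and a table split, with no new data. The statistical downside is some loss of power relative to the three-visit average if benefit persists fully off product, for example 80% against 85% under the assumptions above.

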15.4.5 Efficacy Analyses

All efficacy analyses will be performed on the ITT population and PP population. P-values from analyses of efficacy endpoints must be interpreted in an exploratory fashion since there is no adjustment for multiple endpoints in this study.

The EASI score and other continuous efficacy endpoints will be summarized using descriptive statistics at Baseline, Day 14, Day 28 and Day 42 for actual values and change-from-baseline values. The difference in treatment groups in change-from-baseline values at post-baseline visits will be analyzed using a mixed Analysis of Variance with one between-subject variable (active group vs. vehicle group) and one within-subject variable (Baseline vs. Day 14, Day 28, Day 42). The interaction between within-subject and between-subject variable will be included in the mixed model to test if any difference in treatment groups at post-baseline visits. Outputs from the analysis will include the p-value for the treatment group and interaction factor separately. The p-value should be evaluated at a significance level of 0.05.

Additionally, a one-sided two-sample equal-variance t-test will be performed as a supportive test to analyze the differences in treatment group means in change from baseline at each post-baseline visit (Day 14, Day 28, Day 42). Output from the analysis will include a 95% confidence interval for the difference in treatment groups means at each visit, and the p-values from the hypothesis test of no difference in treatment group means at each visit. The p-value should be evaluated at a one-sided significance level of 0.025.

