### 5. CHANGES TO PLANNED ANALYSES

The definition of per protocol population was changed to be more specific and it would now include only subjects who have the post baseline Day 28 visit instead of any post baseline visit.

Biomarker data and Microbial data will not be analysed at this stage. These are a part of exploratory analysis and would be done later.

29

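### SAP 4.3.1 drops Baseline from the within-subject factor but still says the interaction tests for any treatment difference; on Days 14, 28 and 42 alone it tests only whether the difference varies between visits

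*SAP*

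**What the plan says.** Protocol 15.4.5 analyses change from baseline with treatment arm as the between-subject variable and "one within-subject variable (Baseline vs. Day 14, Day 28, Day 42"). It says that the arm-by-visit interaction serves to test for any arm difference after baseline.

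SAP 4.3.1 changes the factor to "one within-subject variable (Day 14, Day 28, and Day 42") and repeats the purpose sentence unchanged: "The interaction between within-subject and between-subject variable will be included in the mixed model to test if any difference in treatment groups at post-baseline visits". It then lists the model: "The model will include treatment group, siteid and visit as the independent effects and the interaction term" of treatment, visit and site. P-values are to be output "for the treatment group and interaction factor separately". Both documents judge them at the same level; the protocol's words are "The p-value should be evaluated at a significance level of 0.05". A one-sided t-test at each post-baseline visit is added as supportive. SAP 4.3.2 applies a similar model to Skindex 16.

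The shells for EASI, VAS, IGA and Skindex (Tables 14.2.1.1, 14.2.3.1, 14.2.5.1 and 14.2.8.1) carry one p-value footnoted as coming from the mixed-model ANOVA. The term is not named.

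SAP Section 5 lists two changes from the protocol. One concerns the per-protocol set ("it would now include only subjects who have the post baseline Day 28 visit instead of any post baseline visit"), the other the deferral of the biomarker and microbial analyses. The changed within-subject factor is not listed.

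**The concern.** Change at Baseline is zero in both arms by definition. With Baseline as a level, no interaction means that the arm difference is zero at every visit, so the protocol's sentence is correct. Without Baseline, no interaction means only that the arm difference is the same at Days 14, 28 and 42, whatever its size. The sentence was carried over after the change that made it untrue.

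At stake is how a required p-value is read. Someone relying on the sentence could take a non-significant interaction as no evidence of efficacy when the benefit is steady. They could also take a significant one as evidence of efficacy when it shows only that the difference moved between visits, for instance because it faded after treatment stopped at Day 28. The sentence is the only place where 4.3.1 gives a mixed-model term an explicit purpose, so it may also decide which p-value a programmer puts in the tables.

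**Working it through.** **Inputs from the documents** (Protocol 15.1 and SAP 3.1): n = 52 per arm; Day 28 changes of -1.4 (vehicle) and -5.3 (active), a difference of 3.9; SD 7.0. The mixed-model level is 0.05.

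**Assumptions, not in the documents:** SD 7.0 at all three visits; common correlation r between the changes, 0.4/0.6/0.8; arm differences at Days 14 and 42 as given below; complete data; no site effects.

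**The plan's own figure.** Noncentrality = 3.9 / (7.0 × √(2/52)) = 2.84 on 102 df. One-sided 0.025 power is 80.3%, so the stated >80% reproduces.

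**The two null hypotheses.** Let d1, d2, d3 be the arm differences in change at Days 14, 28 and 42, with mean m.
- Protocol, four levels: 0 = d1 = d2 = d3. This is a joint test of no post-baseline difference.
- SAP, three levels: d1 = d2 = d3. A constant benefit satisfies it exactly.

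**Power formulas** (Hotelling noncentral F for the first two, t for the third):
- SAP treatment-by-visit interaction: λ = (n/2) × Σ(dj − m)² / [49(1 − r)], on 2 and 101 df.
- Protocol interaction: λ = (n/2) × {Σ(dj − m)² / [49(1 − r)] + 3m² / [49(1 + 2r)]}, on 3 and 100 df.
- Treatment main effect: noncentrality = m / [SDm × √(2/52)], SDm = 7.0 × √((1 + 2r)/3) = 5.42/5.99/6.52, on 102 df, two-sided.

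**Constant 3.9 at all three visits.**
- SAP interaction: Σ(dj − m)² = 0, so λ = 0 and power = 5% at any n, SD or r.
- Protocol interaction: λ = 26 × 3 × 15.21 / [49(1 + 2r)] = 13.45/11.01/9.31.
- Main effect: noncentrality 3.67/3.32/3.05.

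**Builds up (2.0, 3.9, 3.9).** m = 3.27, Σ(dj − m)² = 2.407. SAP interaction λ = 26 × 2.407 / [49(1 − r)] = 2.13/3.19/6.39.

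**Fades off treatment (2.0, 3.9, 0).** m = 1.97, Σ(dj − m)² = 7.607. SAP interaction λ = 26 × 7.607 / [49(1 − r)] = 6.73/10.09/20.18. Main-effect noncentrality 1.85/1.67/1.54.

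| Arm difference at Days 14, 28, 42 | SAP treatment-by-visit | Protocol four-level interaction | Treatment main effect |
|---|---|---|---|
| 3.9, 3.9, 3.9 | 5/5/5% | 87/79/71% | 95/91/86% |
| 2.0, 3.9, 3.9 | 23/33/60% | 81/78/85% | 86/79/72% |
| 2.0, 3.9, 0 | 62/81/98% | 75/85/98% | 45/38/33% |

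Reversing the second profile to 3.9, 3.9, 2.0 leaves Σ(dj − m)² and the interaction power unchanged: the test does not distinguish a benefit that builds from one that fades.

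**Simulation check.** For the constant benefit, the univariate repeated-measures F (8,000 runs, r = 0.3, 0.5 and 0.8) rejected in 4.9–5.4% of runs with three levels and 81–87% with four.

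**The case against.** The strongest reply is that little is lost. The SAP also outputs the treatment p-value, which for a constant benefit has more power (95/91/86%) than the protocol's interaction (87/79/71%), and the Day 28 t-test on which the trial is sized keeps its stated power. This stands. A reader might infer from the 5% that the efficacy analysis has been crippled, and the documents do not support that.

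The 5% is also a matter of definition rather than an estimate, and it requires the full benefit to persist at Day 42, two weeks after treatment ends. The documents assume a difference only at Day 28. So a reader might infer that an effective drug will usually give a non-significant interaction, but that depends on an unknown time course: under the fading profile the interaction has 62/81/98% power.

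The sentence could also mean that the interaction is included so that the arms can be compared visit by visit, which would be sound and would suit shells that repeat by visit. The SAP does not say so, and it also asks for a separate interaction p-value. On this reading the fault becomes one of ambiguity, and the same edit cures it.

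It might further be inferred that some output is labelled as an interaction test of efficacy. None is; the shells leave the term unnamed. Nor is the 5% shown for the term the model sentence actually lists, treatment by visit by site. That term can also reject because of differences between sites, and the number of sites is not given, so its power was not computed. Adding site still does not turn it into a test for any treatment difference.

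Finally, safety is the primary objective, Protocol 15.4.5 calls efficacy p-values exploratory, and no decision rule uses the interaction. This limits the consequence but does not make the sentence true.

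**Conclusion.** The SAP assigns the wrong purpose to one of its two required mixed-model p-values. This rests on algebra: without Baseline, the treatment-by-visit interaction tests equality of the arm difference across visits, and against a constant benefit its power equals alpha. The other percentages rest on the assumed equal SDs, common correlation and time courses.

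The size of the problem is moderate. Dropping Baseline from a model of change scores is reasonable in itself; keeping the sentence and not recording the change is the fault. The efficacy analysis as a whole is not at 5% power. But the two p-values can point in opposite directions, and which is stronger depends on the time course: the main effect averages in the off-treatment Day 42 visit and falls to 45/38/33% if the benefit has gone by then. The SAP therefore needs to say in advance which p-value answers the efficacy question. At present neither the text nor the shells do.

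**What to change.** 1. In SAP 4.3.1, replace the purpose sentence with: *The treatment\*visit p-value tests whether the treatment difference varies between visits; it is not a test of efficacy.*
2. State which p-value answers the efficacy question: the treatment effect or, if the protocol's overall test is wanted, a joint test that the arm difference in change is zero at Days 14, 28 and 42.
3. Name that term in the footnotes of Tables 14.2.1.1, 14.2.3.1, 14.2.5.1 and 14.2.8.1, which carries through to the tables that repeat them.
4. Record the changed within-subject factor in SAP Section 5.

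The cost is SAP wording and shell footnotes, plus one further statement in the same SAS procedure if the joint test is chosen. No new data are needed.
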